## 16.8 Rationale for Starting Dose and Schedule for Phase II

Starting doses in multiple-dose studies were 25, 50, 75, and 100 mg administered orally once daily with the majority of patients receiving the 50-mg dose. Patients in sunitinib studies have been treated on four different schedules: schedules 4/1 and 4/2 comprised 4 consecutive weeks of daily dosing followed by a 1- or 2-week rest period, respectively, while schedules 2/1 and 2/2 comprised 2 consecutive weeks of daily dosing followed by a 1- or 2-week rest period, respectively. The majority of subjects were treated on schedules 4/2 or 2/2 in phase I studies. Schedule 4/2 has been well tolerated with generally mild to moderate adverse effects at a 50 mg daily dose. Therefore, the recommended starting dose of sunitinib for this study is 50 mg daily administered on schedule 4/2 (daily for 4 consecutive weeks on followed by 2 weeks off).

#### 16.9 Pharmaceutical Data

Supplied: Sunitinib malate is supplied by as 12.5 mg, 25 mg, and 50 mg capsules with mannitol, croscarmellose sodium, povidone, and magnesium stearate. Each opaque plastic bottle contains 28 capsules.

# Capsule strength Description

12.5 mg Swedish Orange, Size 4 hard gelatin capsule

25 mg Swedish Orange/Caramel, Size 3 hard gelatin capsule.

50 mg Caramel, Size 2 hard gelatin capsule

Stability: Shelf life stability studies for sunitinib capsules are ongoing.

Storage: Store at controlled room temperature (15°C to 30°C), and protect from light.

Route of Administration: Oral. Sunitinib malate may be administered without regard to meals.

Patient Care Implications: A yellow discoloration of the skin area may result following direct contact with the capsules. Wash the exposed area with soap and water immediately.

For drug interaction information please see protocol sections 8.4 and Appendix VI.

16.10

Adverse Events

See Section 14.0 for adverse events and reporting requirements.

16.11

Potential Drug Interaction

Sunitinib malate is metabolized primarily by liver enzymes, particularly CYP3A4. CYP3A4 inducers (e.g., rifampin, dexamethasone) and CYP3A4 inhibitors (e.g., grapefruit juice, ketoconazole) should be avoided, and certain potent inhibitors and inducers are contraindicated. Rifampin lowers sunitinib malate Cmax concentration by more than 2-fold. Ketoconazole increases sunitinib malate Cmax by 1.6 fold. Dose reduction with the CYP3A4 inhibitors is recommended, based on clinical symptoms. Concomitant treatment with dysrhythmic drugs, i.e., terfenadine, quinidine, procainamide, disopyramide, sotalol, probucol, bepridil, haloperidol, risperidone, indapamide and flecainide, is not recommended.

See specific instructions regarding permitted / not permitted co-medication for this study in section 8.4.

## APPENDIX I – STUDY CALENDER

APPENDIX I	Pre-							Off						
	Study 11	Wk 116	Wk 2	Wk 3	Wk 4	Wk 5	Wk 6	Wk 7 	Wk 8	Wk 9	Wk 10	Wk 11	Wk 12	Stu dy 
Informed Consent	X		_					,						
Demographics	X													
Medical History	X													
Concurrent Meds	X	X											X	
Physical Exam 	X	X						X						X
Height	X													
Weight 	X	X		X		X		X		X		X		X
Performance Status 	X	X		X		X		X		X		X		X
Urine Pregnancy Test 	X													
CBC w/diff, platelets	X							$X^8$						
PT/INR/PTT 	X	Tw	ice a w	eek				As cli	nically	indicat	ed			
Chemistry 	X							$X^8$						X
TSH, T4, Amylase, Lipase	X							X						
Urinalysis	X							X						
BP and HR measurement 	X	X	X	X	X	X	X	X		X		X		X
EKG	$X^{13}$							$X^9$						
LVEF-MUGA 	$X^{13}$							$X^9$						
Endocrine testing	X							$X^9$						
Primary archival tissue block	X													
Adverse Event evaluation 	Base- line sympto ms	X			•••••					•••••			X	X
Clinical tumour measurement	X	Docu	Repeated every 12 weeks (2 cycles). 15 Documentation (radiologic) must be provided for patients removed from study for progressive disease.					$X^{10}$						
Radiologic evaluation	$X^{14}$								$X^{10}$					

<sup>1 Can be once per cycle at physician's discretion for cycle 3+
 Only for women of childbearing potential
 Only for patients receiving low dose anticoagulants or LNW heparin

 Weekly for cycle 1 then day 1, 15, 29 for cycle 2-3, then can be once per cycle at physician's discretion. Repeat daily if BP > 150/100mm HG if previously within normal limits, or recurrent, persistent (>24 hrs) or symptomatic increase > 20 mm Hg and manage as per protocol. Measurements may be performed more frequently at physician's discretion.

LVEF measurements necessary for patients with class 2 NYHA, piror anthracycline or central thoracic radiation, and at investigator's discretion in patients without cardiac risk factors

Adverse events will be recorded and graded using NCI Common Terminology Criteria for Adverse Events version 3 (CTCAE)

Hematology and biochemistry should be repeated day 1 each cycle prior to sunitinib treatment

EKG, MUGA, endocrine testing (urinary metanephrines, catecholamines, serum chromogranin A) should be repeated on day 1, every two cycles.

 Off study radiologic / tumour measurements is required to confirm response in a patients who go off study with a PR or CR

Within 7 days prior to registration

 4 weeks off protocol

Within 21 days of registration

Within 28 days of registration

At investigator discretion, frequency of CT imaging can be decreased from every 12 weeks to every 4 months (+/- 2 weeks) for patients receiving ongoing study treatment with responding or stable disease.

Measurements do not have to be repeated Cycle 1 Day 1, if screening visit occurred  $\leq$  3 days prior; All cycle day 1 assessments must be within 7 days prior to cycle day 1

<sup>4 Albumin, ALP, Total Bilirubin, Bicarbonate, BUN, calcium, chloride, creatinine, glucose, LDH, phosphate, potassium, total protein, AST, ALT, sodium, calculated creatinine clearance (required only if serum creatinine >ULN, using cockcroft formula), CPK

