#### 8.0 TREATMENT PLAN

### 8.1 Chemotherapy Treatment Plan

### 7.1.1 Drug Administration

Agent Dose Route Schedule sunitinib 50mg PO Daily once for 4 out of 6 weeks (1 cycle = 6 weeks) (4 weeks treatment plus 2 weeks observation). Sunitinib can be administered without regard to meals. Patients should be instructed to take their medication at approximately the same time every day. Doses should be recorded as appropriate on the CRF and patient diary.

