### 8.3.4 Other Non-Hematologic Adverse Events

Event	AE Grade	Dose modification
	or	
	Observation	
Fever, chills, flu-like	Grades 1-4	Maintain dose
symptoms		
	Grades 1 and 2	Maintain dose
Fatigue (lethargy,	Grade 3 *	Hold sunitinib until $\leq$ grade 2, then reduce 1 dose
		level and resume treatment
malaise, asthenia)	Grade 4	Hold sunitinib until $\leq$ grade 2, then reduce 1 dose
		level and resume treatment
	>450 but	Review patient's concomitant medications for
	< 550 msec	QT interval-prolonging agents. Correct any
		electrolyte abnormalities.
		Continue sunitinib at current dose level.

\* If neutrophil and/or platelet counts have not recovered to baseline or better within 3 weeks of dose interruption, the patient is withdrawn from the study \* Recurrent grade 3 events require dose reduction.

QTc Prolongation	≥ 550 msec	Stop sunitinib and any other QT-interval prolonging agents immediately. Correct any electrolyte abnormalities, then  1. If there is a plausible explanation for AE other than sunitinib treatment, resume sunitinib at current dose level.  2. If sunitinib may have contributed to the AE:  Reduce 2 dose levels and restart sunitinib.  If QTc remains <500 msec after 14 days at reduced dose, increase one dose level and continue sunitinib.  If QTc remains <500 msec after 14 days, original
		dose of sunitinib may be resumed.
	Grades 1 and 2	Maintain dose
	Grade 3 *	Hold sunitinib until $\leq$ grade 1, then resume
Hand-foot syndrome		treatment at same dose or reduce 1 dose level
	Grade 4	Hold sunitinib until $\leq$ grade 1, then reduce 1 dose
		level or discontinue treatment
	Grades 1-2	Maintain dose *
AST and/or ALT	Grades 3-4	Sunitinib held until ≤grade 2,then resume at dose
elevation		level-1. If grade 3-4 recurs a 2 nd time, discontinue
(SGOT, SGPT)		sunitinib. Also discontinued if there is no resolution
		to < grade 2 on first episode.
Posterior Reversible	Any occurrence	Cease sunitinib and await recovery with
Encephalopathy Syndrome		symptomatic management. Discontinue treatment.
CPK elevation	Grade 2	Hold sunitinib until ≤ grade 2, then reduce 1 dose level and resume treatment

\* Recurrent grade 3 events require dose reduction.

- Patients requiring a delay of > 4 weeks or > 3 dose reductions should go off protocol therapy but may remain at the principal investigators discretion

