### 9.0 EVALUATION DURING AND AFTER PROTOCOL TREATMENT

### 9.1 Evaluation During Protocol Treatment

Investigation	Timing	Investigation	Timing
History and Physical Exam	Day 1 each cycle 	CBC, differential	Day 1 each cycle (prior to treatment) 
Weight, performance status 	Day 1  , 15, and 29 each cycle	PT/INR/PTT 	Twice weekly for first 3 weeks, then as clinically indicated
Clinical tumour measurements	End of every even numbered cycles	Biochemistry	Day 1 each cycle 
Blood pressure, heart rate 	Weekly for cycle 1  then Day 1  , 15, and 29 each cycle thereafter (assessed by nurse or home monitor)	BUN, serum creatinine/clearance  , sodium, potassium, chloride, bicarbonate, bilirubin, alkaline phosphatase, AST, ALT, LDH, total protein, calcium, phosphate, albumin, glucose, CPK	Day 1 each cycle 
Adverse Events/ Toxicity Evaluation 	Each visit at the end of every cycle	Amylase, Lipase	Day 1 each cycle 
Urinalysis	Day 1 each cycle 	TSH, T4	Day 1 each cycle 
EKG	Day 1 of even numbered cycles 	LVEF  / MUGA	Day 1 of even numbered cycles 
Endocrine testing (urinary metanephrines, catecholamines and serum chromogranin A)	Day 1, every 2 cycles 	CXR or CT 	End of even numbered cycles

Each visit:

 $^{1}$  Repeat daily if BP > 150/100 mmHg if previously WNL, OR recurrent, persistent (> 24Hrs) or symptomatic increase by > 20 mmHg and manage as per Section 8.3.

<sup>2 Only for patients receiving low dose anticoagulants (< 2 mg coumadin, warfarin) or LMW heparin.

 $^{3}$  Only required if serum creatinine is > ULN. Creatinine clearance to be measured directly by 24 hour urine sampling or as calculated by Cockcroft Formula: GFR = 1.04 x (140-age) x weight in kg NB: this version of the formula incorporates a 15% reduction for women

<sup>4 To ensure comparability, baseline xrays/scans/LVEF and subsequent xrays/scans/LVEF to assess response and cardiac effects must be performed using identical techniques.

<sup>5 Adverse events will be recorded and graded using NCI Common Terminology Criteria for Adverse Events Version 3.0 (CTCAE) (Appendix IV)

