## 16.6 Pharmacokinetic and Pharmacodynamic Studies

Clinical pharmacology studies of sunitinib demonstrate that Cmax and AUC increase in a proportional manner after single doses of 50-350 mg, as well as after multiple doses of 25-100 mg (Investigator's Brochure SU011248, 2008). Cmax ranged from 26.0-48.7 ng/mL for the parent compound and from 4.3-8.9 ng/mL for the major metabolite, SU12662. AUC0-24 ranged from 389-819 ng•hour/ml for sunitinib and 52-140 ng•hour/mL for SU12662. Peak plasma concentrations of the metabolite were much lower than those of sunitinib but declined more slowly. The terminal elimination half-lives of sunitinib and SU12662 are approximately 40 hours and 80 hours, respectively. After 28 days of dosing, the AUC0-24 for sunitinib increased 2.5- to 3.5-fold, while AUC0-24 of SU12662 increased 4-to 12-fold compared to day 1. Plasma concentrations of sunitinib and SU12662 typically reach steady-state levels after 1 to 2 weeks of dosing. Concentrations of parent drug and metabolite measured through 3 cycles of therapy have shown that Cmax, AUC0-24, and trough plasma drug concentrations during cycle 2 or cycle 3 were not increased above those observed in cycle 1.

The major in vitro studies on metabolism enzymology have been conducted in human liver microsomes, human hepatocytes, and expressed human CYP enzymes. Sunitinib is primarily metabolized in human liver microsomes by cytochrome P450 (CYP) isoform 3A4 but appears to have minimal potential to inhibit CYP3A4-mediated metabolism, and studies in human hepatocytes indicated that neither sunitinib nor SU12662 induced CYP3A4. These studies suggest that sunitinib and SU12662 are unlikely to have any clinically relevant drug-drug interactions with drugs that are substrates for CYP3A4. Concurrent administration of sunitinib and ketoconazole, a potent CYP3A4 inhibitor, resulted in less than a 2-fold increase in sunitinib exposure (based on Cmax and AUC) and a small decrease in SU12662 exposure (Washington 2003). However, concurrent administration of sunitinib and rifampin (a potent CYP3A4 inducer) in healthy male Caucasian and Asian volunteers resulted in a 4-fold reduction in sunitinib plasma exposure (AUC) and a 2.5-fold reduction in plasma Cmax compared with sunitinib alone in both ethnic groups (Bello 2005).

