Biomarker analysis was performed on plasma samples taken predose on days 1 and 28 of each cycle from 63 patients with MRCC treated with 50 mg sunitinib daily on the 4/2 schedule (DePrimo 2005). After the first cycle, VEGF increased 3-fold in 24 of 54 patients compared to baseline, PIGF increased greater than 3-fold in 22 of 55 patients, and sVEGFR2 levels decreased by 30% in 50 of 55 patients. In addition, longitudinal decreases in sKIT were observed in most cases. Results from this study indicate that analysis of circulating proteins may be of utility as pharmacodynamic biomarkers of sunitinib activity.

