- Cardiac enzymes CK-MB, cTnT, or cTnI were measured in over 200 subjects receiving sunitinib with the expectation that an elevation in cTn accompanying a decline in LVEF would suggest a drug-induced myocardial injury. In contrast, lack of correlation with cTn would be expected from conditions that induce (1) transient effects on LVEF, such as altered preload resulting from dehydration or (2) effects on myocardial contractility without significant myocardial cell injury. Viewed in the aggregate, the composite clinical data showed no consistent correlation between cTn elevations and decreases in LVEF, suggesting that LVEF declines associated with sunitinib treatment were not indicative of a drug-induced myocardial injury. In summary, intensive and prospective cardiac monitoring in 288 subjects receiving sunitinib has not identified major clinical cardiac AEs at the starting daily dose level of 50 mg (Schedules 2/2 or 4/2). While 8 (2.8%) of these 288 subjects developed significant decreases in LVEF, the evaluation of causality was confounded by comorbidities and the lack of a control population. None of these 8 events was of Grade 4 severity or associated with a fatal outcome. In addition, a correlation between LVEF decreases and drug exposure could not be established. Follow-up extending to 6 or more cycles in over 170 subjects showed no trend in cardiac AEs or cardiotoxicity serum biomarkers to suggest a cumulative or long-term adverse effect of sunitinib on cardiac function. Taken together, these findings suggest no increased risk of significant clinical cardiac toxicity for subjects with solid malignant tumours who will be receiving sunitinib treatment in future clinical studies. Moreover, serial and routine LVEF measurements do not appear justified except for patients with known risk factors for cardiac AEs (e.g., NYHA Class II dysfunction at entry or with a history of Class II dysfunction, prior anthracycline exposure, or central thoracic irradiation).

Although QTc-interval prolongation has not been observed in clinical trials, preclinical (in vitro and in vivo) studies indicate that sunitinib has the potential to inhibit the cardiac action potential repolarization process and prolong QTc (Investigator's Brochure SU011248, 2008).

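### No EKG is scheduled in the dosing weeks: every on-study EKG falls 8 to 15 days after the last dose, so first detection of on-drug QTc prolongation depends on unscheduled EKGs

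*Combined protocol and SAP*

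**What the plan says.** Each six-week cycle is described in 7.1.1 Drug Administration (under 8.1) as "4 weeks treatment plus 2 weeks observation". Section 8.3 adds that missed doses are not made up in weeks 5 and 6, so the last dose of a cycle is on Day 28 at the latest.

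The on-study EKG is dated in three places:

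- **Section 9.1:** "Day 1 of even numbered cycles".
- **Appendix I, footnote 9:** "EKG, MUGA, endocrine testing (urinary metanephrines, catecholamines, serum chromogranin A) should be repeated on day 1, every two cycles". The calendar mark is in week 7.
- **Trial Summary:** every 12 weeks, at the end of each even cycle.

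The window for Day 1 assessments is the same in 9.1 (footnote 11) and Appendix I (footnote 16): "All cycle day 1 assessments must be within 7 days prior to cycle day 1". The only other EKG in the calendar is the pre-study one. Weeks 1 to 6 and the off-study column have none.

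On risk, 16.7 reports preclinical evidence that "sunitinib has the potential to inhibit the cardiac action potential repolarization process and prolong QTc". The same sentence says that prolongation has not been observed in clinical trials, and 8.1.3 says so too. Section 8.3.4 sets actions for QTc above 450 msec and at 550 msec or more. The upper band begins "Stop sunitinib and any other QT-interval prolonging agents immediately", and one branch goes on to re-escalate the dose according to the QTc after 14 days at a reduced dose.

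**The concern.** The plan has a QTc rule for patients taking sunitinib, but its scheduled EKGs all fall when the patient has been off drug for more than a week. If any QTc effect rises and falls with drug level, these readings are poorly placed to show it. A symptomless prolongation during the four dosing weeks would be found only if an EKG happened to be done for another reason.

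Two things are at stake. One is patient safety, because the rule in 8.3.4 cannot start until a reading exists. The other is what the trial can say about QTc under its toxicity objective (1.2): a run of unremarkable scheduled EKGs would be weak evidence that QTc is unaffected during dosing.

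**Working it through.** **Inputs.** Last dose on Day 28 (7.1.1 and 8.3). Next cycle Day 1 is Day 43. The Day 1 window opens 7 days earlier, on Day 36 (9.1 and Appendix I). Half-lives are from 16.6: "The terminal elimination half-lives of sunitinib and SU12662 are approximately 40 hours and 80 hours, respectively".

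**Step 1: are the half-lives consistent with the plan's own data?** Section 16.6 says that AUC over 24 hours rises 2.5- to 3.5-fold for sunitinib and 4- to 12-fold for SU12662 after 28 days of dosing. With once-daily dosing, expected accumulation is R = (1 − 2^(−24×28/t)) / (1 − 2^(−24/t)), where t is the half-life in hours.

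- Sunitinib, t = 40: R = 2.94, inside 2.5 to 3.5.
- SU12662, t = 80: R = 5.31, inside 4 to 12.

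The half-lives reproduce the stated accumulation, so they can be used.

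**Step 2: time since the last dose.** Day 36 − 28 = 8 days. Day 43 − 28 = 15 days. Nominal cycle end is Day 42, which is 14 days. For a reading tied to the next Day 1, a dose hold late in the cycle or a late start to the next cycle only lengthens the gap.

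**Step 3: drug remaining.** Fraction left = 2^(−24 × days / t).

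| Days since last dose | Sunitinib (40 h) | SU12662 (80 h) |
|---|---|---|
| 8 | 2^(−4.8) = 3.6% | 2^(−2.4) = 18.9% |
| 14 | 2^(−8.4) = 0.3% | 2^(−4.2) = 5.4% |
| 15 | 2^(−9) = 0.2% | 2^(−4.5) = 4.4% |

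For parent and metabolite together, assume that the AUC ranges in 16.6 (389–819 and 52–140 ng·hour/mL) are day-1 values and scale them by the stated accumulation. The section does not say this, so the result is a range between two extremes:

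- Least metabolite: 819 × 3.5 = 2866.5 and 52 × 4 = 208. Remaining: 4.6% at 8 days, 0.5% at 15 days.
- Most metabolite: 389 × 2.5 = 972.5 and 140 × 12 = 1680. Remaining: 13.3% at 8 days, 2.9% at 15 days.

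**Step 4: what a dosing-week reading would capture.** Section 9.1 already schedules weight and performance status on Days 15 and 29. After 14 doses, the fraction of steady state is 1 − 2^(−14×24/40) = 99.7% for sunitinib and 1 − 2^(−14×24/80) = 94.6% for SU12662. On Day 29, one day after the last dose, 2^(−0.6) = 66% and 2^(−0.3) = 81% of the level at the last dose remain. No EKG is scheduled on either day.

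**The case against.** The timing is hard to dispute, but several points limit what follows from it.

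- **The signal is preclinical.** The documents say twice that QTc prolongation has not been seen in clinical trials. They do not state that any effect depends on concentration; that is an inference from the mechanism in 16.7. This stands, and it limits the weight of the point. It does not remove it, because readings taken largely off drug add little to that record.
- **The 8.3.4 rule is not idle.** Its thresholds apply to any EKG. It also covers co-medication, electrolytes and causes other than sunitinib, which an off-drug reading can reveal. Its 14-day step implies an on-drug EKG, though only after a reading of 550 msec or more has been found. So the gap is in scheduled first detection.
- **There are other safeguards.** Baseline QTc of 500 msec or more is excluded (5.2.6.1), proarrhythmic drugs are barred (5.2.10, 8.4.2), EKGs may be done when clinically indicated (5.2.6.1), and 8.1.3 asks for EKG monitoring with 5-HT3 antagonists. Appendix VII asks for EKG abnormalities to be recorded in patients with hypertension, but schedules no EKG. These reduce the risk; none gives a routine on-drug reading.
- **A Day 1 EKG is not expressly pre-dose.** The window wording points to pre-dose, and a reading after that day's dose would reflect a single dose, not steady state.
- **A pre-cycle check is a reasonable choice.** It informs the decision to start the next cycle. Moving it has a cost, given below.

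**Conclusion.** The point holds as a gap in scheduled detection. Under every version of the schedule, the on-study EKG comes 8 to 15 days after the last dose, with 3.6% to 0.2% of sunitinib and 19% to 4% of SU12662 remaining. None is scheduled in weeks 1 to 4. This rests on the half-lives in 16.6, which agree with that section's accumulation figures, and on dosing that runs to Day 28. The consequence for QTc rests on the further assumption that any effect follows drug level. The primary endpoint is not affected.

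A reader might infer more than the documents support:

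- **That a planned QTc result is biased towards no effect.** Section 11.2 lists no QTc endpoint or analysis. The weakness bears on the general toxicity objective only.
- **That the drug is entirely gone.** Largely washed out is accurate; at the early edge of the window about a fifth of the metabolite remains.
- **That the endocrine samples in the same footnote are equally mistimed.** Sections 10.6 and 11.2 define endocrine response as a drop sustained for more than 12 weeks, for which off-drug sampling is defensible. The renal-cancer study in 16.6 that used "plasma samples taken predose on days 1 and 28 of each cycle" measured VEGF, PlGF, sVEGFR2 and sKIT, not this trial's markers.

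**What to change.** Reconcile the Trial Summary, Section 9.1 and Appendix I (the calendar mark and footnote 9) with each other and with the QTc rule in 8.3.4. Keep the number of scheduled EKGs the same, but have them include readings at an existing attendance during the dosing weeks or immediately at their end. This should apply at least in cycles 1 and 2, where Day 15 and Day 29 assessments are already scheduled. The sponsor's clinicians choose the day, and all QTc thresholds and actions stay with them. Report each QTc reading with the time since the last dose, so that on-drug and off-drug values can be told apart. Leave the endocrine sampling as it is; no new QTc analysis is needed.

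The cost is wording in three places, with no added EKGs. There are two drawbacks. A pre-cycle EKG is displaced wherever a reading is moved. From cycle 3, weight and performance status may fall to once per cycle, and after cycle 3 so may blood pressure (9.1, footnotes 8 and 9); blood pressure may also be taken at home. An on-drug EKG in those later cycles could therefore need an extra clinic attendance, which is why the change is limited to a minimum of cycles 1 and 2.
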